l At screening, baseline, weeks 4 through 48, and week 52 (or final assessment), urine pregnancy tests will be performed on all women prior to study drug administration regardless of childbearing potential.

m Concomitant medication usage will be obtained from the start of screening. Background therapies for SLE may not change from week 44 to week 52.

n Adverse events that are suggestive of anaphylaxis or a drug hypersensitivity reaction will be evaluated as per the Clinical Criteria For Diagnosing Anaphylaxis.

o Eligibility will be validated by a central system.

p C-SSRS will be administered directly to the patient using IRT and assessed using C-SSRS Baseline version at baseline (visit 2) and C-SSRS Since Last Visit version at visits 4 through 16.

q At screening, using IRT each patient will be assigned with a 6-digit personal identification screening number.

r The IRT will be accessed at baseline/start of study drug treatment for drug kit assignment. The IRT will also assign a 5-digit treatment number. In addition, the IRT will be accessed during the study for drug resupply.

s The IRT will be accessed at final visit for study disposition.

t Patients will be randomly assigned to receive a 200-mcg dose of IPP-201101 or placebo. IPP-201101 or placebo will be administered subcutaneously every 4 weeks from weeks 0 to 48. Patients who continue to meet the inclusion/exclusion criteria will be assigned a permanent 4-digit unique randomization number using the IRT. The IRT will assign a 5-digit treatment number. The 1st dose of study drug will be administered at baseline (visit 2) after all assessments have been completed. Patients should be monitored for at least 1 hour after study drug administration at visits 2 and 4 and then at the discretion of the investigator.

u Study drug may not be administered by the same individual performing the SLEDAI-2K, BILAG-2004, PhGA, SFI, and SDI. These disease activity indices must be completed before study drug is administered (at visits at which study drug is administered).

v [PhGA, SLEDAI 2K and SFI are captured on the same form and then assessed in BLIPS software.](#)

V=visit; D=day; W=week; BL=baseline; FV=final visit; ET=early termination; I/E=inclusion/exclusion; PE=physical examination; HBsAg=hepatitis B surface antigen;

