- (k) The patient has an ongoing active systemic infection requiring treatment or a history of severe infection, such as hepatitis or pneumonia, in the 3 months prior to administration of the 1st dose of study drug. Less severe infections in the 3 months prior to administration of the 1st dose of study drug are permitted at the discretion of the investigator and medical monitor.
- (l) The patient has any concomitant medical condition unrelated to SLE that may interfere with his or her safety or with evaluation of the study drug, as determined by the investigator.
- (m) The patient has a history of a medical condition other than SLE that has required treatment with oral corticosteroids in excess of 80 mg of prednisone equivalent/week within 3 months of the 1st dose of study drug.
- (n) The patient has a positive test result for HBsAg or HCV Ab.
- (o) The patient has a known positive history of antibodies to human immunodeficiency virus (HIV) or HIV disease or other immunosuppressive state (eg, agammaglobulinemia, etc).
- (p) The patient has a history of alcohol or substance dependence or abuse (with the exception of nicotine), according to the Diagnostic and Statistical Manual of Mental Disorders of the American Psychiatric Association, Fourth Edition, Text Revision (DSM-IV-TR), within 3 months of the screening visit or has current substance abuse.
- (q) The patient has a history of severe allergic reactions to or hypersensitivity to any component of the study drug or placebo.
- (r) The patient has undergone or is undergoing treatment with another investigational drug for the treatment of lupus within 6 months prior to the 1st dose of study drug or has received any other investigational drug for any other condition within 4 weeks prior to the 1st dose of study drug.
- (s) The patient has previously participated in a clinical study with IPP-201101.
- (t) The patient is a pregnant or lactating woman. (Any women becoming pregnant during the study will be withdrawn from the study.)
- (u) The patient is unlikely to comply with the study protocol or is unsuitable for any other reason, as judged by the investigator or medical monitor.

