##### **7.6.2 Columbia-Suicide Severity Rating Scale**

An evaluation for suicidality will be administered directly to the patient using IRT. (ERT), at baseline and at each visit during the treatment period using the Columbia-Suicide Severity Rating Scale (C-SSRS). The C-SSRS assesses suicidality from ideation to behaviors and monitors the potential emergence of suicidality in clinical studies. The C-SSRS Baseline version will be performed at baseline (visit 2) and the C-SSRS since Last Visit version will be performed at visits 4 through 16 (or final assessment visit).

If the C-SSRS is positive at any visit during the treatment period, the patient will be evaluated by the investigator to determine if a formal evaluation by a trained mental health professional is indicated. If the patient is determined to be a risk to himself or herself or others, the sponsor will be notified and the patient will be withdrawn from the study.

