#### **10.7.2 Safety Variables**

The overall safety and tolerability of IPP-201101 treatment will be assessed throughout the study by evaluating adverse events and the following additional safety variables:

- clinical laboratory (serum chemistry, hematology, and urinalysis) test results at each visit during the treatment period
- vital signs (systolic and diastolic blood pressures, pulse, temperature, and body weight) measurements at each visit during the treatment period
- 12-lead ECG findings at week 24 and the final assessment (or early termination) (week 52)
- suicidality using the C-SSRS at each visit during the treatment period
- adverse events that suggest an anaphylactic reaction to study drug during the treatment period

- physical examination findings, including physical examination symptom directed findings, at selected time points throughout the study
- concomitant medication usage throughout the study

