### **10.7.3 Safety Analysis**

For continuous variables, descriptive statistics (n, mean, SD, median, minimum, and maximum) will be provided for actual values and changes from baseline to each time point, including endpoint. For categorical variables, patient counts and percentages will be provided. Descriptive summaries of serious adverse events, patient withdrawals because of adverse events, and clinically significant abnormal values (clinical laboratory or vital signs values) on the basis of predefined criteria will also be provided. Summaries will be presented by treatment group and for all patients.

All adverse events will be coded using the Medical Dictionary for Regulatory Activities (MedDRA). A patient will be counted only once in each preferred term or system organ class category for the analyses of safety. Summaries will be presented for all adverse events (overall and by severity), adverse events determined by the investigator to be treatment related (overall and by severity), serious adverse events, and adverse events causing withdrawal from the study. Summaries will be presented by treatment group and for all patients. Patient listings of deaths, other serious adverse events, and adverse events leading to withdrawal will be presented.

Changes in laboratory and vital signs measurement data will be summarized descriptively. All values will be compared to prespecified boundaries in order to identify clinically significant changes or values, and such values will be listed.

Newly occurring physical examination abnormalities will be identified and listed.

The use of concomitant medications will be summarized by therapeutic class using descriptive statistics. Concomitant medications will include all medications taken while the patient is treated with study drug. Concomitant medication usage will be summarized as present at screening, ongoing at baseline/start of study drug treatment (visit 2 [week 0]), and started any time after visit 2 (week 0) through visit 16 (week 52).

Cumulative positive C-SSRS outcomes during the study will be summarized by treatment group.

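### The one C-SSRS summary that Section 10.7.3 names does not compare a patient's post-dose result with that patient's visit 2 form, so persisting ideation is counted together with new ideation

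*Protocol*

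**What the plan says.** The schedule (Protocol Table 2, footnote p) calls for the "C-SSRS Baseline version at baseline (visit 2) and C-SSRS Since Last Visit version at visits 4 through 16". The visit 2 form is completed before the first dose. Section 7.6.2 describes the scale as one that "monitors the potential emergence of suicidality in clinical studies".

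Section 10.7.2 lists as a safety variable "suicidality using the C-SSRS at each visit during the treatment period". Section 10.7.3 then gives the only analysis sentence that names the scale: "Cumulative positive C-SSRS outcomes during the study will be summarized by treatment group". The general rules in the same section provide changes from baseline for continuous variables, and counts and percentages for categorical ones.

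The protocol does not define a positive result. Its other use of the word for this scale is the clinical trigger in Section 7.6.2, which also makes no reference to baseline: "If the C-SSRS is positive at any visit during the treatment period, the patient will be evaluated by the investigator".

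**The concern.** Section 7.6.2 asks whether suicidality emerges on treatment. A cumulative count of positives answers a different question: how many patients were ever positive. A patient with ideation at visit 2 that continues onto a Since Last Visit form enters that count exactly as a patient whose ideation begins after dosing. A patient who was already positive and becomes worse adds nothing further to it.

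Such patients can be enrolled. No exclusion criterion in Section 4.2 names suicidal ideation or behaviour. Only judgement-based criteria could apply, such as (l), "The patient has any concomitant medical condition unrelated to SLE that may interfere with his or her safety", and the general unsuitability criterion (u).

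Elsewhere Section 10.7.3 does use the starting point. Concomitant medication is separated into that present at screening, that ongoing at visit 2 and that started later. For physical findings, "Newly occurring physical examination abnormalities will be identified and listed". At stake is how clearly one descriptive safety table can be read.

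**Working it through.** **Text check.** The protocol states no C-SSRS rate, so there is no figure of its own to reproduce. The question is whether any rule links a later result to the patient's own visit 2 form.

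- The C-SSRS sentence in 10.7.3 has no baseline reference and no new-or-worse category.
- The change-from-baseline rule in 10.7.3 covers continuous variables only.
- The categorical rule in 10.7.3 may give counts by visit, possibly including visit 2. Counts by visit compare groups and do not link results within a patient.
- Section 3.1 starts the treatment period at the baseline visit, so a count over the study could include visit 2 positives. That would mix old with new ideation further.

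No reading of the C-SSRS analysis text supplies the within-patient comparison.

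**Illustration of size.** The only input from the protocol is 100 patients per arm (Section 10.2). All rates are assumptions:

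- p0 = share positive at visit 2, from 1% to 20%
- r = share of those still positive on a Since Last Visit form, from 50% to 100%, equal in both arms
- e = rate of new or worse ideation, 1% on placebo and 4% on active, independent of persistence

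Formulas:

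- q = p0 × r
- rate shown by the cumulative count = q + (1 − q) × e
- 95% half-width of the difference = 1.96 × √[a(1 − a)/100 + b(1 − b)/100], with a and b the two rates shown

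Example with p0 = 10% and r = 50%, so q = 0.05:

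- placebo: 0.05 + 0.95 × 0.01 = 0.0595
- active: 0.05 + 0.95 × 0.04 = 0.0880
- difference 0.0285, ratio 1.48
- half-width: 1.96 × √(0.0595 × 0.9405/100 + 0.0880 × 0.9120/100) = 0.072

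| Count | Placebo | Active | Difference (points) | 95% half-width (points) | Ratio |
|---|---|---|---|---|---|
| New or worse only | 1.0% | 4.0% | 3.00 | 4.3 | 4.00 |
| Cumulative, p0 1%, r 50% | 1.495% | 4.48% | 2.985 | 4.7 | 3.00 |
| Cumulative, p0 5%, r 50% | 3.475% | 6.4% | 2.925 | 6.0 | 1.84 |
| Cumulative, p0 10%, r 50% (or 5%, 100%) | 5.95% | 8.8% | 2.85 | 7.2 | 1.48 |
| Cumulative, p0 20%, r 50% (or 10%, 100%) | 10.9% | 13.6% | 2.70 | 9.1 | 1.25 |
| Cumulative, p0 20%, r 100% | 20.8% | 23.2% | 2.40 | 11.5 | 1.12 |

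**Second set of assumptions.** Suppose new ideation arises only in patients negative at visit 2, in 2% on placebo and 6% on active (ratio 3.0). The rate shown is then p0 × r + (1 − p0) × e. With p0 = 10% and r = 50%, this gives 0.05 + 0.90 × 0.02 = 6.8% and 0.05 + 0.90 × 0.06 = 10.4%, a difference of 3.6 points and a ratio of 1.53. Over p0 from 2% to 15% and r from 50% to 100%, the ratio runs from 2.32 down to 1.20. The pattern is the same, and the size follows the inputs.

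**The case against.** **This is for the statistical analysis plan.** The definition of a positive result and the layout of safety tables are commonly settled there, and Section 10.11 refers to a complete statistical plan. This stands in part. A reader might infer that the final analysis will lack a baseline comparison, or that the visit 2 form goes unused. The protocol does not support either: its sentence is not exclusive, and the period covered may include visit 2. The missing definition of a positive result is therefore not pressed here. What remains is that the protocol names a specific summary, and that summary does not separate emergence from persistence.

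**Emergent ideation is already captured as an adverse event.** Section 7.1.1 covers occurrences that develop or worsen, Section 7.1.2 requires all adverse events to be recorded, and Section 10.7.3 summarizes them by arm and severity. Appendix A lists suicidal ideation as grade 4, and Section 3.6 withdraws patients for any grade 4 event. A reader might infer that new or worsened ideation would go unreported; these rules say otherwise, and together with the evaluation rule in 7.6.2 they also limit how long ideation can persist in the study. The backstop is partial because nothing in the protocol requires a positive C-SSRS to be recorded as an adverse event.

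**A new-or-worse count has its own blind spot.** If the drug prolonged existing ideation, the cumulative count would register it and a new-or-worse count would not. The illustration cannot show this, because it assumes equal persistence in both arms. This objection stands in full and determines the form of the fix: add to the cumulative summary, and do not replace it.

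**The effect is small.** In the central example the difference moves by 0.15 points. This also stands. The large fall in the ratio reflects the added common background more than any change in the difference.

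**Conclusion.** The point holds as a minor one. The C-SSRS summary named in Section 10.7.3 counts persisting with new ideation and does not show worsening in a patient already positive, so it fits poorly with the purpose stated in Section 7.6.2.

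Its effect is dilution and wider uncertainty in a descriptive table. Under the first set of assumed rates, the difference stays between 2.4 and 2.985 points against 3.0, while the half-width grows from 4.3 to between 4.7 and 11.5 points. At 100 per arm neither count would be conclusive.

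A reader might infer that the table is biased for or against the drug. The documents do not support that: randomization balances visit 2 ideation in expectation, and equal persistence gives dilution only. The true size is unknown, since every rate used is an assumption. The primary endpoint is untouched.

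**What to change.** Keep the existing sentence in Section 10.7.3 and add after it:

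> The number and percentage of patients with post-dose (Since Last Visit) suicidal ideation or behaviour that is new or worse than the visit 2 Baseline category will also be summarized by treatment group; patients positive at visit 2 will be shown separately, with their post-dose status (resolved, persisting or worse).

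The separate display keeps any drug-prolonged ideation in view. The cost is one sentence of analysis wording and one more table. Both versions of the form are already collected, so no new data, visits or patients are needed.

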## **10.8 Pharmacokinetic and Immunogenicity Analysis**

IPP-201101 plasma concentration data will be summarized by time point. Plasma concentration data may also be included in population pharmacokinetic analyses.

An attempt may be made to establish an exposure-response relationship and/or to correlate systemic exposure with relevant safety parameters. In order to perform the exposure-response analysis successfully, it is extremely important that the actual collection times for pharmacokinetic blood samples be recorded accurately.

The immunogenicity of IPP-201101 will be evaluated by determining any presence of anti-IPP-201101 Ab at weeks 2, 4, 12, 20, 28, 36, and 44 and the final assessment (week 52 or early termination). Testing results will be listed and findings may be summarized as necessary.

## **10.9 In vitro intracellular and secreted cytokine response**

In vitro intracellular and secreted cytokine response data will be summarized by time point.

In vitro intracellular and secreted cytokine response of IPP-201101 will be evaluated to assess secreted cytokine profile and intracellular modification linked to the treatment at weeks 0, 4, 24 and 48. Testing results will be listed and findings may be summarized as necessary.

## **10.10 Planned Interim Analysis**

There is no planned interim analysis.

## **10.11 Reporting Deviations From the Statistical Plan**

Deviations from the statistical plan, along with the reasons for the deviations, will be described in protocol amendments, the complete statistical plan, the clinical study report, or any combination of these, as appropriate.

## **11 DIRECT ACCESS TO SOURCE DATA/DOCUMENTS**

The medical experts, study monitors, auditors, and health authority inspectors (or their agents) will be given direct access to source data and documentation (eg, medical charts/records, laboratory test results, printouts, videotapes) for source data verification, provided that patient confidentiality is maintained in accordance with local requirements.

Each investigator must maintain, at all times, the primary records (ie, source documents) of each patient's data. Examples of source documents are hospital records, office visit records, examining physician's finding or notes, consultant's written opinion or notes, laboratory reports, drug inventory, study drug label records, and CRFs that are used as the source (see section 3.9).

Each investigator will maintain a confidential patient identification list that allows the unambiguous identification of each patient. All study-related documents must be kept until notification by ImmuPharma.

## **12 QUALITY CONTROL AND QUALITY ASSURANCE**

### **12.1 Protocol Amendments and Protocol Deviations and Violations**

#### **12.1.1 Protocol Amendments**

No changes from the final approved (signed) protocol will be initiated without the prior written approval or favorable opinion of a written amendment by the IEC/IRB, except when necessary to eliminate immediate safety concerns to the patients or when the change involves only logistics or administration. Each principal investigator and the sponsor will sign the protocol amendment.

### **12.1.2 Protocol Deviations, Violations, and Exceptions**

A **protocol deviation** is nonadherence to protocol-specific study procedures or schedules that does not involve inclusion/exclusion criteria, primary objective variable criteria, and/or GCP guidelines. Deviations are considered minor and do not impact the study. For example, failure to perform scheduled study center visits within the protocol-defined window would be considered a deviation.

A **protocol violation** is any significant divergence from the protocol, ie, nonadherence on the part of the patient, the investigator, or the sponsor to protocol-specific inclusion/exclusion criteria, primary objective variable criteria, and/or GCP guidelines. Protocol violations will be identified and recorded, by study center personnel, on the CRF.

As a matter of policy, ImmuPharma or its designee will not grant **exceptions** to protocol-specific entry criteria to allow patients to enter a study. If under extraordinary circumstances such action is considered ethically, medically, and scientifically justified for a particular patient, prior approval from ImmuPharma or its designee and the responsible IRB/IEC, in accordance with the Standard Operating Procedure (SOP), is required before the patient will be allowed to enter the study. If investigative center personnel learn that a patient who did not meet protocol eligibility criteria was entered in a study (a protocol violation), they must immediately inform ImmuPharma or its designee. Such patients will be discontinued from the study, except in a rare instance following review and written approval by ImmuPharma or its designee and the responsible IRB/IEC, according to the applicable SOP.

### **12.2 Information to Study Personnel**

Each investigator is responsible for giving information about the study to all staff members involved in the study or in any element of patient management, both before starting the practical performance of the study and during the course of the study (eg, when new staff become involved). Each investigator must assure that all study staff members are qualified by education, experience, and training to perform their specific responsibilities. These study staff members must be listed on the study center authorization form, which includes a clear description of each staff member's responsibilities. This list must be updated throughout the study, as necessary. The study monitor is responsible for explaining the protocol to all study staff, including each investigator, and for ensuring their compliance with the protocol. Additional information will be made available during the study when new staff become involved in the study and as otherwise agreed upon with either the investigator or the study monitor.

### **12.3 Study Monitoring**

To ensure compliance with GCP, the study monitor or representative is responsible for ensuring that the study is conducted according to applicable SOPs, the protocol, and other written instructions and regulatory guidelines.

The study monitor is the primary association between the sponsor and each investigator. The main responsibilities of the study monitors are to visit each investigator before, during, and after the study to ensure adherence to the protocol, that all data are correctly and completely recorded

and reported, and that informed consent is obtained and recorded for all patients before their participation in the study.

The study monitors will contact each investigator and visit the study center at regular intervals throughout the study. The study monitor will be permitted to check and verify the various records (CRFs and other pertinent source data records, to include specific electronic source documentation [see section 3.9]) relating to the study to verify adherence to the protocol and to ensure the completeness, consistency, and accuracy of the data being recorded. If electronic case report forms (eCRFs) are used for the study, the study monitor will indicate verification by electronically applying source document verification (SDV) flags to the eCRF and will ensure that all required electronic signatures are being implemented accordingly.

As part of the supervision of study progress, other sponsor personnel may, on request, accompany the study monitor on visits to the study center. Each investigator and assisting staff must agree to cooperate with the study monitor to resolve any problems, errors, or possible misunderstandings concerning the findings detected in the course of these monitoring visits.

